Official Title:	Multicenter open-label randomized comparative trial of the efficacy and safety of single bolus injection of Fortelyzin® («SuperGene», LLC) and bolus-infusion of Actilyse® (Boehringer Ingelheim Pharma GmbH) in patients with massive pulmonary embolism (PE)
Short title:	FORPE
Trial phase:	III b
Trial aim:	Assessment of the efficacy and safety of single-bolus intravenous injection of Fortelyzin® in comparison with bolus infusion of Actilyse® in patients with massive PE
Trial objectives:	
• To assess the efficacy of single-bolus intravenous injection of Fortelyzin® in comparison with bolus infusion of Actilyse® in patients with massive PE• To assess the safety and possible adverse events of single-bolus intravenous injection of Fortelyzin® in comparison with bolus-infusion of Actilyse® in patients with massive PE
Trial design:	A multicenter, open-label, randomized, comparative, parallel-group non-inferiority trial of efficacy and safety. In clinical centers, patients will be randomized using the «envelope method» into two equal groups of 155 patients each (a total of 310 people, including 10 % of those who may have dropped out) and assigned to receive either Fortelyzin® or Actilyse®. The drugs will be administered after signing the informed consent. Fortelyzin® in a dose of 15 mg

	
will be given as single i.v. bolus over 10-15 seconds. Actilyse® will be administered in accordance with the instruction for use. Patients will be monitored for 30 days: 1-2 days in the Intensive Care Unit and the Department of cardiology in the remaining days before discharge (on average 14 days), with an outpatient visit on the 30th day.
 
Enrollment of patients into the trial will be conducted on a competitive basis.

Trial duration:	The trial completion date is the 30th day after the final trial patient was included in the trial. All patients will be examined for 30 days
Trial population:	Men and women aged 18 years and older with a diagnosis of massive PE
Sample size:	The total number of patients included in the trial – 310 people, including 10 % of possible dropouts

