8. DESIGN AND PLAN OF RESEARCH ACTIVITIES

This trial is a multicenter, open-label, randomized, parallel-group, phase III b non-inferiority trial to compare the efficacy and safety of the trial drug.

The trial will include 310 patients with massive PE. The patients will be monitored for 30 days: 1-2 days in the Intensive Care Unit and the Department of cardiology in the remaining days before discharge (on average 14 days), with an outpatient visit on the 30th day.

Start of research, initiation of centers: «_____» 20____

Enrollment of patients: «_____» 20____

Result processing and reporting: «_____» 20____

The enrollment period may be extended to total patient enrollment if a research center fails to enroll the planned number of patients. The end date of the trial is considered to be the end date of the trial in all patients involved.

In each research center, the subject of the trial is assigned a serial number that corresponds to the sequence of patient inclusion in the trial. The serial number is reflected in the CRF. The list of patient's identification is stored in the trial file. Patients are included in the trial only after signing the Informed consent form.

Before the trial, all patients will undergo the following procedures: collection of thorough medical history, signs of hemodynamic collapse, risk stratification to assess the prognosis according to the PESI classification, a physical examination, CTPA, ECG, EchoCG with the definition of PASP, ultrasound diagnostics of the inferior vena cava will be performed; blood and urine samples will be taken for laboratory tests:

- **complete blood count:** hemoglobin, red blood cells, hematocrit, leukocyte formula: neutrophils, eosinophils, basophils, monocytes, lymphocytes, platelets, ESR;
- **biochemical blood parameters:** total protein, creatinine, urea, AST, ALT, CK, NT-proBNP, total bilirubin, glucose, sodium, potassium, total cholesterol, HDL-cholesterol, triglycerides;

- **coagulogram:** fibrinogen, aPTT, INR, prothrombin, D-dimer.
- **general urine analysis:** red blood cells.

After enrollment, patients will be randomized using the «envelope method» into two equal groups of 155 patients each (a total of 310 people, including 10% who may have dropped out) and assigned to receive either Fortelyzin® or Actilyse®. Fortelyzin® will be given as single i.v. bolus over 10-15 seconds. Actilyse® will be administered following the instruction for use.

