11. EFFICACY ENDPOINTS

- Primary efficacy outcome – death from any causes within 7 days;
- Secondary efficacy outcome – PASP (V1, V2, V4, V5);
- Secondary efficacy outcome – hemodynamic collapse within 7 days;
- Secondary efficacy outcome – recurrent PE within 7 days;
- Secondary efficacy outcome – death from PE within 7 days;
- Secondary efficacy outcome – death from any causes within 30 days;
- Secondary efficacy outcome – clinical composite of hemodynamic collapse within 7 days + recurrent PE within 7 days + death from any causes within 30 days.

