17. SAMPLE SIZE CALCULATION

In the Russian Federation, multicenter randomized clinical trials of PE thrombolytic therapy have not previously been conducted. The largest clinical material of PE thrombolysis – 236 patients over 15 years – was collected in the Faculty of Surgery Clinic of N.I. Pirogov Russian National Research Medical University [1].

The calculation of the number required was carried out taking into account the capacity of 80 % and planning of a non-inferiority study in parallel groups [10]. The null hypothesis (H_0) was that the thrombolytic therapy with Fortelyzin® is inferior to the standard thrombolytic therapy with Actilyse®. This means that frequency of the primary efficacy criterion in the comparison group (P_{Actilyse}) is higher than in the group of the study drug ($P_{\text{Fortelyzin}}$) (δ):

$$H_0: P_{\text{Fortelyzin}} - P_{\text{Actilyse}} \leq -\delta$$

The alternative hypothesis (HA) is that Fortelyzin® therapy is non-inferior to the standard thrombolytic therapy with Actilyse:

$$H_A: P_{\text{Fortelyzin}} - P_{\text{Actilyse}} > -\delta$$

The calculation of the sample size for the “non-inferiority” hypothesis, the primary criterion representing the proportion of respondents, and even 1:1 distribution in therapy groups is carried out according to the following formula [11]:

$$n = \frac{(z_{1-\alpha} + z_{1-\beta})^2}{(\delta - \Delta)^2} [p_1(1 - p_1) + p_2(1 - p_2)]$$

where n – the number of patients in each of the groups compared;

p_1 – the proportion of respondents (reaching the primary efficacy criterion) in the group of the study drug;

p_2 – the proportion of respondents in the comparison group with Actilyse®;

$\Delta = p_1 - p_2$ – the expected difference between the proportions of respondents in the groups of the study drug and the comparison drug;

δ – “non-inferiority” boundary

α and β – probabilities of type I and II errors, respectively;
 $Z_{1-\alpha}$ and $Z_{1-\beta}$ – critical values of the standard normal distribution.

The limit of clinical significance was chosen to be 10% and was calculated as follows.

According to published results, hospital mortality from massive PE without treatment is 30% [12]. Since placebo control is unethical and given the characteristics of the disease (the insignificant role of the placebo effect is obvious), the absence of treatment can be considered equivalent to the placebo effect.

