In-hospital mortality after thrombolysis with bolus and bolus-infusion alteplase ranges from 8% to 13,4% with an average of 10% [13, 14].

The expected mortality in both treatment groups is 10%. The clinically acceptable difference limit was chosen to ensure that at least 50% of the effect of the comparator drug relative to placebo/no treatment is retained. Thus, the difference between mortality is $(30\% - 10\%) / 2 = 10\%$. With a planned study power of 80% and a one-sided confidence interval of 2,5%, the minimum number of patients enrolled in the study is estimated to be 141 patients per treatment group to maintain 80% power for the comparison. Taking into account a possible 10% dropout rate, the sample size was increased to 310 patients to 155 patients in each group.

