18. STATISTICAL ANALYSIS OF TRIAL RESULTS

All indicators entered into the clinical database will be listed for each patient and sorted by group (Fortelyzin® or Actilyse®), patient number and visit.

Statistical analysis was carried out using R Foundation for Statistical Computing и Graph Pad Prism 7, Graph Pad Software Inc (version 4.2). Continuous variables will be presented as mean (SD) or median (IQR). Categorical variables will be presented as n (%) and corresponding 95% Clopper-Pearson confidence intervals (CI).

Mann-Whitney U test will be used to compare continuous variables and the two-sided Fisher's exact test will be used to compare categorical variables.

Odds ratios (ORs) will be estimated and presented with 95% CIs. Outcomes will be considered as statistically significant if the p value will less than 0,05.

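### Section 18 contains no non-inferiority test: 7-day death would be compared by a two-sided Fisher test and an odds ratio, and the 10-point margin behind the sample size is never used

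*Combined protocol and SAP*

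**What the plan says.** The protocol summary describes the design as "A multicenter, open-label, randomized, comparative, parallel-group non-inferiority trial of efficacy and safety", and Section 8 repeats this: "phase III b non-inferiority trial to compare the efficacy and safety of the trial drug". Section 11 names the endpoint: "Primary efficacy outcome – death from any causes within 7 days".

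Section 17 sets null and alternative hypotheses on the difference between the two arms' proportions, with a boundary δ. It then fixes that boundary: "The limit of clinical significance was chosen to be 10% and was calculated as follows". The reasoning is that mortality is 30% untreated and 10% on alteplase, and that "at least 50% of the effect of the comparator drug relative to placebo/no treatment is retained", so the margin is half of the 20-point effect. The sample size uses a one-sided 2.5% level and 80% power.

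For a binary outcome, Section 18 lists:

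- counts and percentages with 95% Clopper-Pearson intervals;
- a test: "the two-sided Fisher's exact test will be used to compare categorical variables";
- an effect measure: "Odds ratios (ORs) will be estimated and presented with 95% CIs";
- a decision rule: "Outcomes will be considered as statistically significant if the p value will less than 0,05".

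Section 18 does not mention the margin, a risk difference, a one-sided 2.5% criterion, or a separate analysis of the primary endpoint. Sections 19 and 20 do not add any of these.

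**The concern.** Fisher's test asks whether the two death rates are equal. Non-inferiority asks whether the excess on Fortelyzin can be shown to be less than 10 points. A significant Fisher result shows a difference. A non-significant one may only reflect imprecision, and it does not bound the excess.

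The other tools in Section 18 do not close the gap. The Clopper-Pearson intervals describe each arm's own proportion. The odds ratio is on a different scale from the margin, and no odds-ratio margin is given.

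The primary outcome is death and the trial is open-label. An analyst following Section 18 would have to choose the effect scale, interval method and success rule afterwards, or treat a non-significant p-value as evidence of similarity. Either would undermine the confirmatory claim.

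**Working it through.** **Inputs.** From Section 17: 10% expected mortality in both arms, margin δ = 0.10, one-sided α = 0.025, power 80%, 1:1 allocation, 141 per arm raised to 155 for 10% dropout, and published alteplase mortality of 8% to 13.4%. From Section 18: two-sided Fisher test, p < 0.05.

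**1. The plan's own sample size.** With p₁ = p₂ = 0.10 and Δ = 0, the Section 17 formula gives

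n = (1.960 + 0.842)² × (0.09 + 0.09) / 0.10² = 7.849 × 0.18 / 0.01 = 141.28.

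This matches the stated 141 (rounding up would give 142), and 141 × 1.1 = 155.1 matches 155. At one-sided 5% the formula gives 112, so 2.5% is the level used. The trial size therefore rests on testing a risk difference against 10 points.

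**2. What the Section 18 test does.** Two independent binomial arms were enumerated exactly and the two-sided Fisher p-value computed for every table.

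| True mortality (Fortelyzin, Actilyse) | Per arm | P(Fisher p ≥ 0.05) |
|---|---|---|
| 10%, 10% | 141 | 96.8% |
| 10%, 10% | 155 | 96.6% |
| 20%, 10% (at the margin) | 141 | 40.2% |
| 20%, 10% (at the margin) | 155 | 35.3% |

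Under the planning assumption of equal mortality, Fisher gives p < 0.05 in only about 3% of trials (1.7% in favour of Fortelyzin at 155 per arm). The stated 80% power therefore does not belong to this test. If p ≥ 0.05 were read as non-inferior, the rows at the margin give the false-claim rate, against 2.5% planned.

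**3. An example.** Take 24 deaths against 16 with 155 per arm (15.5% and 10.3%, a difference of 5.2 points). Fisher p = 0.24. The upper limit of the 95% Newcombe interval for the difference is +12.7 points (Wald +12.6). Non-inferiority is not shown, but the Section 18 outputs would not reveal that.

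**4. The odds ratio at the margin.** For control mortality p, OR = [(p + 0.1)/(0.9 − p)] / [p/(1 − p)].

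- p = 8%: (0.18/0.82)/(0.08/0.92) = 2.52
- p = 10%: (0.20/0.80)/(0.10/0.90) = 2.25
- p = 13.4%: (0.234/0.766)/(0.134/0.866) = 1.97

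No single odds ratio represents the 10-point margin.

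**5. What a matching test delivers.** The rule is that the upper limit of the two-sided 95% interval for Fortelyzin minus Actilyse lies below +10 points (exact enumeration).

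| Per arm | Interval | Power at 10%, 10% | Type I error at 20%, 10% |
|---|---|---|---|
| 141 | Newcombe | 78.0% | 2.6% |
| 155 | Newcombe | 82.0% | 2.6% |
| 141 | Wald | 79.8% | 2.7% |
| 155 | Wald | 83.3% | 2.7% |

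**The case against.** The best defence is that Section 17 already contains the framework: hypotheses on the difference, a 10-point boundary and a one-sided 2.5% level. Section 18 is a short generic paragraph that neither calls Fisher the primary test nor abandons the margin, so a reader could infer the intended rule. It is true that the margin and hypotheses exist. But Section 17 uses the 2.5% level only for sizing and names no interval method or decision rule, and the tools in Section 18 are for a different question. Nor can Section 17 be applied literally. Its null, Fortelyzin minus Actilyse at or below −δ, is written for a favourable outcome. With death as the event, the direction is reversed.

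A second objection is that the 35–40% figure describes one possible misuse, since no section says that p ≥ 0.05 means non-inferior. That is right: as written, the plan has no non-inferiority rule to which an error rate could be attached. The figure shows the cost of the most likely way of filling the gap.

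A third objection is that 82% power assumes all 155 per arm are evaluable. With 10% missing, about 139 or 140 remain and Newcombe power is 77–78%. This stands as a small qualification. Section 7.4 keeps randomised non-completers in the analysis, which favours the higher figure if vital status at day 7 is known.

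**Conclusion.** The concern holds, with high confidence, and must be fixed. The sample size reproduces only as a test of a 10-point risk difference at one-sided 2.5%, while Section 18 specifies a test of equality and an effect measure on another scale. This is an analysis of the wrong hypothesis for the stated aim, not just a missing detail.

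Read as evidence of non-inferiority, a non-significant Fisher result would pass a drug at the margin in 35% of trials at 155 per arm and 40% at 141. These figures assume 10% control mortality, independent binomial arms and complete outcome data, and they are conditional on that reading. The mismatch between Sections 17 and 18 depends on none of these assumptions.

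**What to change.** Add a primary-analysis paragraph to Section 18 along these lines: the risk difference in all-cause death within 7 days (Fortelyzin minus Actilyse) will be estimated with a two-sided 95% confidence interval by the Newcombe method, and non-inferiority will be concluded if the upper limit is below +10 percentage points. Miettinen-Nurminen, or another valid interval for a difference, would serve as well, provided it is named in advance. State the primary analysis set in the same paragraph. Keep Fisher's test and the odds ratio as supportive for the primary endpoint and as tests of difference for secondary and safety outcomes.

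In the same amendment, restate the Section 17 hypotheses for death as an unfavourable event: the null is a difference of at least +δ and the alternative a difference below +δ.

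The cost is protocol and SAP wording. The planned 310 patients can stay: Newcombe power is 82% if all 155 per arm are evaluable and 77–78% if 10% are lost, so near-complete day-7 vital status keeps it above 80%.

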19. MONITORING AND AUDIT

Monitoring and audit will be conducted by the Ministry of Health of the Russian Federation in accordance with the requirements of the GCP. At the same time, Investigators should provide direct access to the clinical sites' documentation and medical documentation.

In order to ensure that all the requirements of the Protocol are met, monitoring visits will be carried out periodically during the trial. A clinical site may also be subject to inspections by other Regulatory Authorities. The primary medical documentation will be checked to verify its compliance with the data entered in the CRF.

National Regulatory Authorities may conduct audits during and after the trial.

The audit may include but is not limited to, monitoring of the correct storage and delivery of the study drug, availability of necessary documentation, compliance with procedures of signing the Informed consent form, CRFs management, compliance with the Protocol of the trial as a whole, and comparison of data reflected in the CRFs with the information included in the primary documentation.

Prior to the start of the trial, the Monitor should conduct an initiating visit to the clinical site to ensure that all materials (CRF, study drug, etc.) have been received by the center in proper condition, and to train the Investigator and the center's staff to comply with the procedures and requirements of the Protocol.

Monitoring of the research center can be carried out through visits and telephone contacts. The monitor of clinical research will perform monitoring visits in accordance with a pre-determined schedule and with sufficient frequency to assess the rate of patient's inclusion, verification of data entered in the CRF in comparison with the data of the primary documentation, monitor the compliance with the Trial Protocol and the study drug handling.

After the completion of participation of all patients, the Monitor will conduct a final visit.

Efficacy and safety results will be analyzed by an Independent Data Monitoring Committee (Steering committee) when 25%, 50% and 75% patient enrollment will be reached.

20. REPORTING

Each clinical site compiles a report, which is signed by the Principal Investigator and approved by the head of the medical institution on the basis of which the center is located.

The statistical processing is carried out by an independent statistical expert on the basis of the CRF.

The deadline for report submission is up to one month after the completion of the trial.

The final report will contain clinical and statistical reports, as well as appendixes with individual data and statistical analysis.

The suggested structure of the report: the purpose of the trial, methods (including any deviations from the Trial Protocol), evaluation of the results, discussion of adverse events, and their interpretation.

